Cover page for Clinical Trials Document

Study title	Establishment of Reference Intervals of Complete Blood Count and Coagulation Tests in Pregnant Women at Hung Vuong Hospital
NCT Number	NCT05929326
Document date	August 27, 2023

I. STUDY PROTOCOL

Reference intervals are defined as the 2.5th percentile to 97.5th percentile of a normal population. Therefore, it is common to interpret results as abnormality based on normal reference intervals in pregnant women due to their biophysiological changes [1]. As a result, it is crucial to define normal reference intervals for pregnant women. Complete blood count and coagulation tests such as activated partial thromboplastin time (APTT), prothrombin time (PT), and fibrinogen are of a routine hematology panel. There have been many studies conducted on Asian pregnant women [2, 3], but none was conducted in Vietnam. Therefore, we conduct this study to determine trimester specific reference intervals for healthy pregnant women.

Patient selection

From June 2023 to August 2023, pregnant women visiting obstetrics clinics at Hung Vuong Hospital are selected if eligible after history taking and clinical examination. Inclusion criteria was singleton pregnancy. Exclusion criteria were hypertension, diabetes, pre-eclampsia, gestational diabetes, hemoglobinopathy, current infection, positive screening for *treponema pallidum*, hepatitis B virus, HIV, usage of anticoagulant drug. Each patient will have their blood drawn 4 millimeters (mL), 2 mL into citrate anticoagulated tube to test for APTT, PT, fibrinogen, and 2 mL into Ethylenediaminetetraacetic acid (EDTA) tube to test for complete blood count.

To establish reference intervals using non-parametric method, the minimum sample size needed is 120, according to CLSI EP28-A3c [4], because of the 90% confidence interval reported for the 2.5th percentile. However, Sample Sizes for Clinical, Laboratory and Epidemiology Studies [5] suggested a calculation for larger minimum required sample size

$$N_{Rank} = \eta \sqrt{3} \times \left[\frac{z_{1-\gamma/2}}{\rho_{plan} \times z_{1-\gamma/2}} \right]^2 \text{ where } \eta = \frac{\sqrt{(\gamma/2)[1-(\gamma/2)]}}{\phi_{1-\gamma/2}} = 2.11 \quad (\phi_{1-\gamma/2} = \frac{1}{\sqrt{2\pi}} e^{\frac{z_{1-\gamma/2}^2}{2}})$$

with $\alpha = 0.05$, $\gamma = 0.1$. ρ_{plan} is margin of error, which is the estimate of the percentage that the width of the confidence interval of the reference limits is of the width of the reference interval. The recommended ρ_{plan} is 10%. From the formula above, the calculated sample size required is 258 patients. Because we want to establish trimester specific reference intervals, the total combined number of each trimester is at least 774 patients.

Ethical approval

The study was approved by the Ethical committee of Hung Vuong Hospital, Vietnam. Written consent was obtained before study participation.

Samples collection and instrument

Venous blood samples were collected in trisodium citrate 3.2% and K₂EDTA plastic whole blood tube and then immediately analyzed.

Instrument and analysis

Coagulation assays, which comprises of Activated partial thromboplastin time (APTT), prothrombin time (PT), fibrinogen (FIB), was performed on ACL TOP 550 automated coagulation analyzer (Werfen, Barcelona, Spain) and complete blood count, including White blood cell (WBC) counts and percentage and absolute count of different

leukocytes (neutrophils, lymphocytes, monocytes, eosinophils and basophils), red blood cells (RBC), hemoglobin (Hgb), hematocrit (HCT), mean corpuscular volume (MCV), mean corpuscular hemoglobin (MCH), mean corpuscular hemoglobin concentration (MCHC), RBC distribution width (RDW), platelet counts (PLT), mean platelet volume (MPV), was performed on DxH900 automated hematology analyzer (Beckman Coulter, CA, USA).

All instruments were maintained and calibrated according to the manufacturer's instruction. Two levels of controls were done on ACL TOP 550 analyzer every eight-hour shift and three levels of controls were run DxH900 once a day.

II. STATISTICAL ANALYSIS PLAN

Patients are divided into three groups, based on their gestational age. The three groups are the first, second and third trimester. The non-parametric method, recommended to establish reference intervals by CLSI EP28-A3c, is used to determine the lower reference limit 2.5th percentile and upper reference limit 97.5th percentile for each group. Each reference limit was reported along with its 90th confidence interval. Groups are then compared using Mann-Whitney U and Kruskal-Wallis tests. A two-tailed P-value < 0.05 was considered significant.

REFERENCES

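### The single 10% precision figure rests on a normal density; at 258 per trimester the expected 90% CI is about 14–16% of the reference interval for a Gaussian analyte, and wider at the upper limit if the analyte is right-skewed

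*Combined protocol and SAP*

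**What the plan says.** The sample-size text under Patient selection (section I) gives a formula called N_Rank and defines its precision parameter as "the estimate of the percentage that the width of the confidence interval of the reference limits is of the width of the reference interval". The value adopted is 10%, with α = 0.05 and γ = 0.1, and "the calculated sample size required is 258 patients" per trimester, so at least 774 in total. The density in the formula is written out as the standard normal density. No other distributional information enters, and one target serves both limits of every analyte.

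The SAP (section II) says: "The non-parametric method, recommended to establish reference intervals by CLSI EP28-A3c, is used" to find the 2.5th and 97.5th percentiles in each trimester, each with a 90% CI. It plans no transformation, no check of distribution and no precision by analyte. Under Instrument and analysis the protocol lists 3 coagulation tests, the total white-cell count, 5 leukocyte types as percentages and as absolute counts, and 9 red-cell and platelet indices: 3 + 1 + 5 + 5 + 9 = 23 analytes.

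**The concern.** A distribution-free method needs no normality to estimate a percentile. The width of its CI, however, is governed by how many observations lie near that percentile, that is, by the analyte's density there. Planning with a normal density gives equal precision at both limits. For a right-skewed analyte the upper tail is thinner, relative to the reference interval, than the normal one, so the upper limit is less precise and the lower limit more precise than a single figure suggests.

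Reference limits are the product of this study. A reader who takes 10% as the precision of all of them would be too confident in every limit if the analytes are Gaussian, and most of all in the upper limits of any skewed analyte, which are the limits used to call a value high.

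**Working it through.** **Inputs from the protocol.** α = 0.05 (z = 1.960); γ = 0.1 (z = 1.645); target ratio 0.10; η = 2.11; 258 per trimester.

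**Reproducing 258.** Read the z in the denominator as the one for α and the exponent of the density as negative. The printed symbols differ, which may be a typing or text-extraction artefact and is not counted here.

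- η = √(0.05 × 0.95) / φ(1.645) = 2.113
- N = 2.113 × √3 × [1.645 / (0.10 × 1.960)]² = 257.8, rounded up to 258
- 3 × 258 = 774

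The plan's figures therefore reproduce.

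**Precision of a rank-based limit at n = 258.** For the p-th percentile q of an analyte with density f, the large-sample ratio is

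2 × 1.645 × √(p(1−p)) / [f(q) × √258] ÷ (reference-interval width).

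The limits are the 2.5th and 97.5th percentiles, so √(0.025 × 0.975) / φ(1.960) = 2.671 applies.

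**Gaussian analyte.** In SD units the CI width is 2 × 1.645 × 2.671 / √258 = 0.547 and the reference interval is 2 × 1.960 = 3.920. The ratio is 0.547 / 3.920 = 14.0% at both limits. The value differs from 10% because the plan's η takes the density at the 95th percentile rather than the 97.5th, and because N_Rank carries η√3 where the large-sample variance gives η². A ratio of 10% would need 258 × (0.1396/0.10)² ≈ 503 per trimester.

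**Right-skewed analyte (assumption: log-normal with log-scale SD σ).** The density at the upper limit q = exp(1.96σ) is φ(1.96)/(σq), and the reference-interval width is exp(1.96σ) − exp(−1.96σ). The upper-limit CI width is 0.547 × σ × q.

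- σ = 0.25: 0.223 / 1.020 = 21.9%
- σ = 0.5: 0.729 / 2.289 = 31.8%

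**Order-statistic check.** The 90% CI by binomial ranks uses observations 247 and 256 (upper limit) and 3 and 12 (lower limit), with actual coverage 92.7%. Mean widths come from 20,000 simulated samples. Numerical integration of the expected order statistics agrees to within about 0.1 percentage point.

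| Assumed shape | Upper, large-sample | Upper, order-statistic | Lower, large-sample | Lower, order-statistic |
|---|---|---|---|---|
| Normal | 14.0% | 16.1% | 14.0% | 16.1% |
| Log-normal, σ = 0.1 | 16.9% | 19.7% | 11.4% | 13.1% |
| σ = 0.2 | 20.1% | 23.6% | 9.2% | 10.4% |
| σ = 0.25 | 21.9% | 25.8% | 8.2% | 9.3% |
| σ = 0.4 | 27.6% | 33.1% | 5.8% | 6.5% |
| σ = 0.5 | 31.8% | 38.5% | 4.5% | 5.0% |

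The pattern does not depend on the log-normal form: gamma shapes from 8 to 1 give upper-limit ratios of 20.8–34.9% (large-sample) or 24.3–41.4% (order-statistic).

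**Share due to skew.** On the large-sample basis the step from 10% to 14.0% is common to all analytes. Skew adds the step from 14.0% to 16.9% at σ = 0.1, to 21.9% at σ = 0.25 and to 31.8% at σ = 0.5.

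**The case against.** - **The skew is assumed.** A reader might infer that several of these analytes, such as the differential white-cell counts, are known to be right-skewed. The documents give no SD, skewness or pilot data, and no σ can be tied to a named analyte. This objection stands: the skewed figures are conditional and must be shown as a range. The normal shape that the plan applies to all 23 analytes is equally unsupported.
- **Skew explains the whole gap.** A reader might infer that 258 delivers 10% for Gaussian analytes and that only skewed ones miss it. It does not: the Gaussian ratio is already 14–16%. At σ = 0.1 skew adds only about 3 percentage points.
- **The plan contradicts itself.** It does not. A normal working density is a legitimate way to plan a rank-based CI, the stated 258 and 774 reproduce, and 10% is called a recommended value rather than a guaranteed one. The problem is an unstated assumption and a precision figure that does not follow from the sample size.
- **Trimester differences will be misread.** A reader might infer that sampling error in the limits will pass for physiology. The SAP reports a 90% CI with every limit, so the imprecision is shown. Its Mann-Whitney and Kruskal-Wallis tests compare groups and do not test the limits against each other. The achieved ratio can be computed from the planned output, so printing it adds convenience rather than new information.
- **The order-statistic widths are inflated by over-coverage.** Partly so. Ranks 3 and 11, and their mirror image at the upper limit, cover 89.6% and give about 24% rather than 26% for the upper limit at σ = 0.25. The conclusion is unchanged.

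**Conclusion.** The point holds in a conditional form. The stated 10% is not what 258 women per trimester are expected to deliver for the CIs that the SAP plans. For Gaussian analytes the ratio is 14.0% (large-sample) to about 16% (order-statistic) at both limits. That part needs no assumption beyond the plan's own normal density.

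If an analyte is right-skewed, one figure for both limits no longer describes it. Under a log-normal shape with log-scale SD 0.1 to 0.5, the upper limit is at about 17–32% (large-sample) or 20–38.5% (order-statistic), and the lower limit at about 11% down to 4.5%, or 13% down to 5%. Whether any analyte lies in that range cannot be settled from the documents. The estimation method is sound and the sample size need not change; what needs correcting is the precision claimed for it.

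**What to change.** 1. Keep 258 per trimester. In the sample-size text, replace the 10% with the expected precision: about 14–16% of the reference interval at both limits for approximately Gaussian analytes, and about 17–38.5% at the upper limit under the stated log-normal assumption. Say that the normal density is a working assumption. Do not write that 10% holds for Gaussian analytes, because it does not.
2. In the SAP, define the achieved ratio (90% CI width divided by the estimated reference-interval width) and print it beside each limit.
3. Do not attach a cut-off that labels limits as provisional. With exactly normal data, roughly one sample of 258 in five would exceed twice the planned value at the upper limit by chance.
4. Optionally, for analytes that are Gaussian after transformation, add a transformed-parametric limit as a supplement. At σ = 0.25 the large-sample upper-limit ratio would be 21.9% × √2.92 / 2.671 = 14.0%.

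The cost is a few sentences and one extra table column, and the stated precision becomes less favourable. Enlarging the study to reach 10% is not proposed: on the large-sample basis it would take about 503 women per trimester for Gaussian analytes, and at the upper limit about 1,237 at σ = 0.25 and 2,616 at σ = 0.5.

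### The sample-size formula does not support the stated 10% precision: with Gaussian data, 258 women per trimester give about 14%

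*Combined protocol and SAP*

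**What the plan says.** The sample-size text is under Patient selection in the protocol part.

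- It first cites a guideline for non-parametric reference intervals: "the minimum sample size needed is 120". It then turns to a textbook formula that asks for more.
- That formula multiplies η√3 by a squared bracket. η is built from γ/2 and given as 2.11. The settings are α = 0.05 and γ = 0.1.
- ρ_plan is called a margin of error and then defined as "the estimate of the percentage that the width of the confidence interval of the reference limits is of the width of the reference interval". Its value is set next: "The recommended ρ_{plan} is 10"%.
- The result: "From the formula above, the calculated sample size required is 258 patients". Three trimesters give at least 774.

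The SAP fixes what is estimated. The non-parametric method "is used to determine the lower reference limit 2.5th percentile and upper reference limit 97.5th percentile for each group", and "Each reference limit was reported along with its 90th confidence interval" (read here as a 90% CI).

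**The concern.** Two parts of the formula do not match the quantity that the plan says it controls.

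1. η should describe the sampling error of the percentile being estimated. The study reports the 2.5th and 97.5th percentiles, so the tail is α/2 = 0.025. The plan uses γ/2 = 0.05, which is the tail of the 90% CI. That value of η belongs to the 5th and 95th percentiles, which the study does not report.
2. A CI width is proportional to η/√N, so the N for a given width must be proportional to η². The plan has η√3.

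The 10% target is the plan's reason for going beyond 120. If 258 does not meet it, the stated precision is one that the design does not have. Readers will find the published CIs wider than planned with no explanation, and others may reuse 258 as the size for 10% precision.

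**Working it through.** **Inputs, all from the documents.** α = 0.05, so the limits lie at tails of 0.025 and z(0.975) = 1.9600. γ = 0.1, so z(0.95) = 1.6449. ρ_plan = 0.10, full CI width over full interval width.

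**Quantile factor.** η(p) = √[p(1−p)]/φ(z_p), with φ the standard normal density.

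- p = 0.05: 0.21794/0.10314 = 2.113. This is the plan's 2.11.
- p = 0.025: 0.15612/0.05845 = 2.671, and η² = 7.136.

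**Reproducing 258.** The bracket is K = [1.6449/(0.10 × 1.9600)]² = 70.43. Then 2.113 × 1.732 × 70.43 = 257.8, rounded up to 258. With η rounded to 2.11 the result is 257.4, also 258.

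This takes z(1−α/2) in the denominator of the bracket. The text available to me shows z(1−γ/2) in both numerator and denominator; the two would cancel and N would be 2.113 × 1.732 × 100 = 366. The exponent of φ also appears without its minus sign. Both may come from the reading of the PDF, and I treat neither as an error. The tail and the √3 are not reading errors, because 258 is reproduced with them.

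**Formula implied by the definition of ρ_plan.** With Gaussian data of standard deviation σ:

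- large-sample 90% CI width of a rank-based limit = 2 × z(0.95) × ησ/√N
- reference-interval width = 2 × z(0.975) × σ
- ratio: ρ = z(0.95) × η/[z(0.975) × √N]
- solved for N: N = η² × [z(0.95)/(ρ × z(0.975))]², with η at 0.025

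| Version | N per trimester |
|---|---|
| Plan: η(0.05) × √3 | 257.8 → 258 |
| Power corrected only: η(0.05)² | 314.5 → 315 |
| Tail corrected only: η(0.025) × √3 | 325.9 → 326 |
| Both corrected: η(0.025)² | 502.6 → 503 |

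**Precision obtained, Gaussian, large-sample:** ρ = 1.6449 × 2.671/(1.9600 × √n).

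| n | ρ |
|---|---|
| 120 | 20.5% |
| 258 | 14.0% |
| 366 | 11.7% |
| 503 | 10.0% |

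**Exact rank-based CIs, Gaussian** (mean width over true interval width, by integration over the order statistics).

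| n | Ranks | Coverage | ρ |
|---|---|---|---|
| 258 | 3 and 11 | 89.6% | 15.0% |
| 258 | 3 and 12 | 92.7% | 16.1% |
| 503 | 8 and 20 | 90.5% | 10.3% |
| 503 | 7 and 20 | 93.8% | 11.8% |

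At 258, ranks 3 and 12 are the narrowest pair with at least 90% coverage.

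**Skewed analytes.** The documents give no distributions, so I assume log-normal data over a range of log-SD. Large-sample ρ at n = 258:

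| Log-SD | Lower limit | Upper limit |
|---|---|---|
| 0.1 | 11.4% | 16.9% |
| 0.2 | 9.2% | 20.1% |
| 0.3 | 7.3% | 23.7% |
| 0.4 | 5.8% | 27.6% |

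At log-SD 0.3, ranks 3 and 12 (and their mirror images at the upper end) give 8.3% for the lower limit and 28.1% for the upper.

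**The case against.** **The source may print η√3.** The cited textbook is not available, so I cannot say whether the √3 is the source's, a transcription slip, or the product of another derivation. That uncertainty stands. It does not rescue the number: the formula must agree with the plan's own definition of ρ_plan, and η at 0.05 does not belong to a 2.5th percentile under any multiplier.

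**The term margin of error suggests a half-width.** On that reading 258 would give 14.0%/2 = 7.0%, and 10% would need only 502.6/4 = 125.6, or 126. But the plan goes on to define ρ_plan as one width over another, and I follow that definition. The initial label is loose and worth removing.

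**The formula as printed gives 366.** That is not the number the plan adopts, and 366 would still give 11.7%.

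**Little depends on it.** This largely stands. No reference limit or test uses ρ_plan, 258 exceeds the cited minimum of 120, 774 is stated as a minimum, and the reported CIs will show the precision achieved. Recruitment is given as June to August 2023 and the document is dated August 27, 2023, so the correction comes late. These points limit the remedy to wording; they do not make the 10% statement true.

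**Conclusion.** The concern holds. The figure of 258 rests on an η taken at the wrong tail and entered with the wrong power, and it does not deliver 10% on the plan's own definition. With Gaussian data the CI of each limit at 258 is about 14.0% of the interval width in large samples, or 1.4 times the stated figure. Exact rank CIs give 15.0–16.1%, or 1.5 to 1.6 times. The large-sample Gaussian size for 10% is 503 per trimester.

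The size of the shortfall depends on the Gaussian model. Under the log-normal range assumed above, the upper limit is less precise (16.9–27.6%), while the lower runs from 11.4% down to 5.8% and meets 10% once skewness is moderate. The reference intervals remain valid. What should be fixed is the sample-size justification.

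**What to change.** In the sample-size paragraph:

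1. Replace the formula with N = η² × [z(1−γ/2)/(ρ_plan × z(1−α/2))]², where η = √[(α/2)(1−α/2)]/φ(z(1−α/2)) = 2.67. Check the multiplier against the cited textbook, and drop the term margin of error in favour of the width definition.
2. Keep 258 per trimester and 774 in total, and restate the precision. Suggested wording: *With 258 women per trimester, the 90% CI of each reference limit is expected to be about 14% of the reference-interval width (Gaussian, large-sample), or about 15–16% for exact rank-based CIs depending on the ranks. For right-skewed analytes it will be wider for the upper limit and narrower for the lower.*
3. If 10% is still mentioned, give 503 per trimester as the large-sample Gaussian figure only, since exact rank CIs at 503 still give about 10.3–11.8%.

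The cost is one paragraph of wording and a less favourable stated precision. No patients are added and the analysis does not change.

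### The sample-size formula uses η√3 where the protocol's own definitions require η², so 258 per trimester does not deliver the stated 10% precision

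*Combined protocol and SAP*

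**What the plan says.** The sample-size text is in the protocol part, under Patient selection. It cites a guideline minimum of 120 for the non-parametric method, "because of the 90% confidence interval reported for the 2.5th percentile", and then adopts a larger number from a formula credited to a sample-size textbook. The formula multiplies η√3 by a squared bracket of normal quantiles and ρ_plan. It defines η as √(p(1−p)) over the normal density, evaluates it at γ/2, and gives 2.11. It sets α = 0.05 and γ = 0.1.

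The protocol describes ρ_plan as an estimate of "the percentage that the width of the confidence interval of the reference limits is of the width of the reference interval", and sets it at 10%. The result is: "From the formula above, the calculated sample size required is 258 patients". Three trimesters make at least 774.

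The Statistical Analysis Plan names only the non-parametric method, which "is used to determine the lower reference limit 2.5th percentile and upper reference limit 97.5th percentile for each group", each with a 90% interval. Neither part derives the η√3 multiplier.

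**The concern.** A sample size set by the width of a confidence interval must scale with the square of the standard-error factor. Here η is that factor for a percentile estimated by ranks, yet the formula is linear in η. No argument in the documents turns the second η into √3.

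The 10% figure is the only quantified precision target in the plan, and it is the basis for going from 120 to 258 per group. If the study report repeats that the limits were sized for 10%, it will state a design property that the design does not have.

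**Working it through.** **Inputs.** From the protocol: α = 0.05, so z(0.975) = 1.960; γ = 0.10, so z(0.95) = 1.645; ρ = 0.10; η = 2.11 (2.113 before rounding), taken at p = γ/2 = 0.05. From the SAP: limits at the 2.5th and 97.5th percentiles, non-parametric, with 90% intervals.

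**1. Reproduce 258.** The bracket as it reads in the text has the same z above and below. Taken literally, it gives 2.11 × 1.732 × 100 = 365.5, or 366. With z(0.95) over z(0.975) it is

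K = [1.645 / (0.10 × 1.960)]² = 70.43,

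and 2.11 × 1.732 × 70.43 = 257.4 (257.8 with unrounded η), which rounds up to 258. So the stated number depends on √3, and √3 is not a fault of text extraction.

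**2. Derive the factor from the protocol's definitions.** The large-sample standard error of a percentile is √(p(1−p)) / (f√N), where f is the density at that percentile. For a Gaussian analyte this is ησ/√N. Therefore:

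- width of the limit's confidence interval = 2 × 1.645 × ησ/√N
- width of the reference interval = 2 × 1.960 × σ
- ρ = 1.645 η / (1.960 √N)
- N = η² × K

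Simulation check (20,000 Gaussian samples, N = 258): the standard deviation of the estimated 2.5th percentile was 0.167σ. With η at p = 0.025, η/√N predicts 0.166σ. A variance factor of η√3 predicts 0.134σ.

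**3. Separate the two errors.** The limits are at p = α/2 = 0.025, but the protocol takes η at γ/2 = 0.05. At p = 0.025, η = √(0.025 × 0.975) / 0.05845 = 2.671.

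| η | Multiplier | N for ρ = 10% |
|---|---|---|
| 2.113 (p = 0.05) | η√3 (as planned) | 258 |
| 2.113 | η² | 4.466 × 70.43 = 314.5, so 315 |
| 2.671 (p = 0.025) | η√3 | 4.627 × 70.43 = 325.9, so 326 |
| 2.671 | η² | 7.136 × 70.43 = 502.6, so 503 |

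**4. Precision obtained (asymptotic, Gaussian).**

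- Multiplier error alone, protocol's η, N = 258: ρ = 1.645 × 2.113 / (1.960 × 16.06) = 11.0%.
- η corrected, √3 kept, N = 326: ρ = 1.645 × 2.671 / (1.960 × 18.06) = 12.4%.
- Both errors, N = 258: ρ = 1.645 × 2.671 / (1.960 × 16.06) = 14.0%.

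**5. Sensitivity to the interval method and to shape.** If equal-tailed exact ranks are used at N = 258, they are ranks 3 and 12, with 92.7% coverage; the simulated mean ρ is 16.1%. For lognormal values with log-SD 0.2 to 0.4 (an assumption, not in the documents), the same ranks give about 6% to 10% at the lower limit and 24% to 33% at the upper.

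**The case against.** Several stronger readings are tempting, and the documents do not support them.

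- **That the √3 slip by itself costs the whole gap from 10% to 14% or more.** It does not. With the protocol's own η, ρ at 258 is 11.0%. The further step to 14.0% comes from taking η at the 5th percentile. If that error is reported as a separate point, the 14.0% must not be counted twice.
- **That the achieved figure is 16%, or that 258 fails because few samples reach 10%.** The SAP gives no rank or interpolation rule, and part of the 16% is the 92.7% coverage of the discrete ranks. On the same basis, 503 would also miss: its exact ranks give about 10.3% to 11.8%, depending on the rule. The protocol treats ρ as a planning estimate and sets no probability of attaining it.
- **That √3 was borrowed from the parametric limit.** The variance factor of a parametric limit, 1 + 1.96²/2 = 2.92, is close to 3, so this is possible. The documents give no derivation, and the cited textbook was not available. Whether the slip lies in the source or in the transcription cannot be settled, and the fix does not depend on it.
- **That the reference intervals are unsound.** Nothing in the plan implies this. 258 is more than twice the 120 that the protocol cites, 774 is a floor, and every limit is to be reported with its interval, so readers will see the precision actually obtained.

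The last point carries weight on severity. It does not rescue the 10% claim. Reading ρ as a half-width would (258 then gives about 7%), but the protocol defines it as width over width.

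**Conclusion.** The point holds. The factor that follows from the protocol's definitions of η and ρ is η², and 258 per trimester does not give 10% precision for the limits that the SAP estimates. The multiplier's own effect is modest: 11.0% instead of 10% with the protocol's η, or 12.4% at N = 326 once η is taken at the right percentile. The joint effect with the η error is about 14.0% at 258, and 10% would need about 503 per trimester.

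These figures are asymptotic and assume a roughly Gaussian analyte, which is the protocol's own planning assumption because its η uses the normal density. Exact-rank intervals are somewhat wider. Skewed analytes will have unequal precision at the two limits.

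This is a should-fix: a stated design property is wrong, but no estimate, test or reported interval changes.

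**What to change.** In the sample-size text under Patient selection:

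1. Replace η√3 by η², with η evaluated at the 2.5th percentile (η = 2.671, η² = 7.14), and print the bracket with z(1−γ/2) over ρ_plan × z(1−α/2).
2. Keep enrolment at 258 per trimester and delete the claim that this achieves 10%.
3. State the planned precision instead. Suggested wording: With 258 women per trimester, the 90% confidence interval of each reference limit is expected to be about 14% of the width of the reference interval (large-sample calculation, Gaussian analyte). Exact-rank intervals will be somewhat wider, and for skewed analytes the precision will differ between the lower and upper limits.

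Correcting η alone is not enough, because the formula would then give 326 and still miss 10%. The cost is a few sentences and a less favourable stated precision, with no extra patients and no change to the analysis.

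### Do rank tests between trimesters leave a gap, given that the study's product is the 2.5th and 97.5th percentiles?

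*Combined protocol and SAP*

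**What the plan says.** The introduction to the Study Protocol gives an estimation objective: "Therefore, we conduct this study to determine trimester specific reference intervals for healthy pregnant women". The Statistical Analysis Plan fixes the groups: "The three groups are the first, second and third trimester". It states that the non-parametric method "is used to determine the lower reference limit 2.5th percentile and upper reference limit 97.5th percentile for each group", and adds: "Each reference limit was reported along with its 90th confidence interval" (plainly a 90% interval). The comparison of trimesters takes two sentences: "Groups are then compared using Mann-Whitney U and Kruskal-Wallis tests" and "A two-tailed P-value < 0.05 was considered significant".

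The sample size, set out under Patient selection, rests on the width of a limit's confidence interval relative to the width of the reference interval: "From the formula above, the calculated sample size required is 258 patients". This is multiplied by three to give at least 774. No power or effect size is given for the rank tests. No hypothesis, purpose or decision rule is attached to them anywhere, and no estimate of the between-trimester difference in a limit is planned.

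**The concern.** The quantities of interest lie in the tails, whereas Mann-Whitney and Kruskal-Wallis ask whether values tend to be higher in one group than in another. The two can disagree in both directions. If the spread differs but the medians do not, the limits differ and the rank test has essentially no power. If a small shift and a small change in spread offset each other at one end, the rank test can be significant although one limit has not moved.

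A significance threshold with no stated purpose therefore invites two misreadings: that P ≥ 0.05 lets two trimesters share limits, or that P < 0.05 shows a relevant change in both limits. At stake would be the conclusion about how trimesters differ, and in the worst case a decision to merge intervals that should stay separate.

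**Working it through.** **1. Does the sample size depend on these tests?** Inputs from the protocol: γ = 0.10, α = 0.05, ρ = 0.10.

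- η = √(0.05 × 0.95) / φ(1.645) = 2.113 (the protocol gives 2.11).
- N = η√3 × [1.645 / (0.10 × 1.960)]² = 257.8, rounded up to 258; 3 × 258 = 774.

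The stated figures reproduce. (As printed, the same z stands above and below the line and would cancel, giving 366. The value 258 needs the α-based z in the denominator. That is a separate typographical matter.) No term involves a between-trimester test, so the size rests only on the precision of the limits.

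**2. How far can the rank test and the limits disagree?** The documents give no distributions, so these are assumptions: normal data, 258 per group, reference group with mean 0 and SD 1, comparison group with SD r and mean shifted by d, two-sided 5% tests. Simulation used 3,000 to 4,000 replicates; ranges cover repeat runs.

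- Difference in upper limits = d + 1.96(r − 1).
- Large-sample standard error of that difference = 2.671 × √((1 + r²)/258), where 2.671 = √(0.025 × 0.975)/φ(1.960).
- r = 1.3: 0.588 / 0.273, power 58%. r = 1.5: 0.980 / 0.300, power 90%. d = 0.25: 0.25 / 0.235, power 19%.
- Share outside the reference group's interval with equal medians = 2[1 − Φ(1.96/r)]: 13.2% for r = 1.3 and 19.1% for r = 1.5. For d = 0.25: 4.4% above and 1.4% below.
- Planned 90% intervals for a limit: 3rd and 12th order statistics from each end, actual coverage 92.7%.

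| Assumed truth | Mann-Whitney rejects | Power, direct test of upper limit | Planned CIs of upper limit disjoint | CIs of at least one limit disjoint |
|---|---|---|---|---|
| No difference | about 6% | (nominal 5%) | 1.3% | 2.5% |
| r = 1.3, equal medians | 5.4–6.1% | 58% | 34–35% | 57–58% |
| r = 1.5, equal medians | 4.7–5.0% | 90% | 75–77% | 94–95% |
| r = 1, d = 0.25 | 79–81% | 19% | about 7% | not computed |

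Identical upper limits: r = 0.9 with d = 1.96 × 0.1 = 0.196. The lower limits are then 0.196 − 1.764 = −1.568 and −1.960, which is 0.39 SD apart. Mann-Whitney rejects in 62–65%, although the upper limits coincide.

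The rank test is therefore not a test of the limits.

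**3. Does the plan use it as one?** Each step of the SAP against its dependence on the rank tests:

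- Division into three groups: by gestational age, before any test.
- Percentiles and their intervals: computed within each group, with no input from the tests.
- Rank tests: run after the intervals are set, with no later step conditional on the result.

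There is no merging rule and no claim of equivalence. Each trimester's two limits are reported with intervals, so the direction and size of a difference in either limit can be read by subtraction.

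**The case for a change.** The strongest case for a change is that the plan attaches a significance threshold without calling the tests descriptive, so a misreading is not ruled out. Comparing published intervals by eye is informal, and non-overlap is conservative. For the upper limit at r = 1.3, the intervals separate in 34–35% of studies, whereas a direct comparison has 58% power. At r = 1.2, even counting either limit, they separate in only 28%. One could add bootstrap intervals for differences in limits, and the percentage of women outside another trimester's interval, without recruiting anyone.

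All of that is true as description, but it does not show that a planned result is wrong. The protocol lists 23 measurands (3 coagulation, white cells, 10 differential, 9 others), so the addition means 23 × 3 pairs × 2 limits = 138 differences. The 95% interval for an upper-limit difference would be about 0.95 SD wide. With so many, they would have to be reported without significance claims, so they would supply no decision rule either. Under a shift, which is what a rank test is built to find, the direct limit comparison is much the weaker tool: 16–19% against about 80% at 0.25 SD, and 54–57% against more than 99% at 0.5 SD. The extra table is a reasonable supplement for authors who want it, but it corrects nothing.

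**Conclusion.** No change to the plan. The description of the rank tests is right: they address overall shift, their purpose is unstated, and they can miss or misplace differences in limits. But followed as written, the plan yields sound trimester-specific limits with intervals, plus valid tests of whether values shift between trimesters. The harm needs a reader or analyst to draw a conclusion that the plan nowhere authorises. Pooling trimesters after a non-significant result would depart from the stated objective and from the sizing of 258 for each of three groups.

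The unstated purpose is missing detail that analysts fill sensibly by treating the P-values as descriptive. Its effect on the limits, their intervals and the 774 total is nil. That conclusion rests on the text and needs no distributional assumption. The simulated percentages do: they assume normality and equal groups of 258, and the spread ratios and shifts are illustrative, since the documents do not say which of them are realistic for these analytes.
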